Improvements in cardiorespiratory fitness in response to exercise training varies greatly between individuals, with some people responding well or very well ('responders' or 'high-responders') to exercise training, whereas others only have mild increases in their cardiorespiratory fitness following similar exercise training ('low-responders') [2-4, 23, 24]. The ability to change cardiorespiratory fitness is a multifactorial trait [2, 4]. Considering cardiorespiratory fitness is one of the best integrative predictors of morbidity and mortality risk, it is important to understand how factors, such as genetics and environmental influences (e.g. training and diet), may predict the variability in response to exercise training. This knowledge could lead to targeted personalised exercise therapy to decrease the burden of chronic disease.

Predictor genes for $\dot{V}O_{2\max}$ trainability

From our systematic review, 35 studies identified 97 genes that predict $\dot{V}O_{2\max}$ trainability [6]. Exercise-related phenotypes are complex traits and are polygenic (i.e. influenced by many genes working together) with each genetic variant likely to be contributing a small percentage (typically less than 1%) to the overall change in $\dot{V}O_{2\max}$.

Approximately, 50% of the variance in $\dot{V}O_{2\max}$ trainability can be attributed to genetic make-up. A gene predictor score (GPS) based on these variants can predict who may be a lower or higher responder to training. A score of '0' represents homozygote (two copies of the same allele) for the low-response variant; '1' represents heterozygous (two different alleles, with one a high response allele) and '2' represents homozygous for the high-response allele. Individuals with a low score (e.g. <9 high response alleles) may be a lower responder to training.

Possible Gene Expression Mediators

Training intervention

HIIT has a lower frequency of 'non-responders' [7]; and greater improvements in vascular function, cardiorespiratory fitness and other biomarkers compared to other forms of training [7, 25]. This training requires individuals to exercise at a high intensity (e.g. 90% of maximum heart rate) for a specific period of time (e.g. 4 minutes) with a rest/recovery period (e.g. 3 minutes) in between [26].

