Participants will be recruited through Exercise Physiology Brisbane channels (where principal investigator works) channels. These channels will include current patients, Facebook, emails, face-to-face, doctor's surgeries) using referrals, email, newsletters and snowballing (see appendix for wording). Additionally, an email will be sent out to current staff and students from the University of Queensland. This process will begin once ethics has been approved and continue until 40 people have been recruited (within a 12-month time-frame).

Inclusion Criteria

- Inactive adults aged between 18 and 50 years
- Less than 60 minutes of structured exercise each week
- Signed consent form

Exclusion Criteria

- Antibiotic use 6 months prior to intervention or antibiotic use during intervention.
- Pre- or-probiotic use within four weeks of participating in study
- Pregnancy, chronic infections, auto-immune diseases and intestinal chronic conditions (e.g. IBS, Crohn's disease, ulcerative colitis, coeliac disease).
- Existing cardiac conditions
- Recent surgery or orthopaedic conditions that prevents treadmill walking/running

- Diabetes
- Allergies to inulin (chicory root) or fructans
- Allergies to maltodextrin and other polysaccharides
- Allergies to soy, milk and egg (there maybe traces of these in maltodextrin)
- Greater than 60 minutes of exercise per week within four weeks of the study

Rationale for Criteria

Antibiotics can decrease gut microbiome diversity [35]. As such, participants on antibiotics up to 6 months prior to the study will be excluded. Moreover, pre-and probiotics may alter gut composition; participants on these supplements (up to four weeks prior) will be excluded. The age and exercise inclusion criteria have been added to create a more homogenous group. Other exclusions are included for participant safety (e.g. to avoid exacerbating existing conditions or placing the participant at a greater risk for a health complication).

Informed consent

Through the recruitment, information will include details about the study and the above-mentioned inclusion and exclusion criteria. The contact details for the Research Team will be provided.

Once participants have registered their interest and the Research Team check they meet the inclusion criteria, they will be asked to sign the informed consent form (via email or posted) and to come to the University of Queensland for the following baseline testing sessions.

Baseline testing sessions

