All non-coded records will be stored in a locked filing cabinet with restricted access for a minimum of five years in a private office of [name]. Any information obtained for the purpose of this research project that can identify a participant will be treated as confidential and securely stored. All computer records will be stored on an access-restricted and file-encrypted network (UQ's Research Data Management System). Only the Principal Investigator and Co-Investigators will have access to project's documents. It will be disclosed only with permission, or as permitted by law.

Data Collection

Primary outcomes

A panel of genetic variants will be identified from a saliva sample collected at baseline via an Oragene collection kit. Saliva samples will be sent to the Translational Research Institute (TRI) for DNA extraction and GWAS analysis. The GWAS will target predictor genes identified from our PREDICT HIIT study.

GWAS analysis

a) DNA extraction from saliva

DNA will be extracted from the stabilised saliva samples using the QIASymphony (Qiagen) DNA MIDI Kit (Cat.no. 937255). The yield and purity will be measured using the Trinean DropSense-96 as per the manufacturer's instructions.

b) Genotyping

100ng of DNA will be genotyped on Illumina Infinium HumanCoreExome24v1.1 arrays as per manufacturer's instructions. The arrays will be scanned on an Illumina iScan system and the raw fluorescence intensity data normalized and clustered for each sample using Illumina Genome Studio (v. 2011.1). Genotypes will be called using the standard Illumina HumanCoreExome24v1.1 cluster file.

c) GWAS

The program PLINK will be used to convert the .ped and .map files into .fam, .bim and .bed files. To this data, clinical files (co-variables and phenotypes) will be added. Data is filtered via the following steps: 1) sample level (call rate, heterozygosity, relatedness, ancestry), 2) SNP level (call rate, minor allele frequency, HWE). Two new types of data will be created: 1) principal components for capturing population-substructure, and 2) genotypes of untyped SNPs (using sanger imputation server for the imputations with HRC r1.1 as reference). Logistic regression will be performed with 'N' PCA components (N is unknown until we do the experiments). SNP coordinates are from the Genome Reference Consortium GRCh37 (hg19) build. A Manhattan plot will be created to visualise the significant genetic markers and raw density plot will be examined manually.

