The following table outlines the information to be collected.

Measure	Pre	Post
Cardiorespiratory Fitness		
VO _{2peak}	X	X
Resting blood pressure	X	X
Resting heart rate	X	X
Maximum heart rate	X	X
Gene Predictor Score		
Total number of variants that contribute to high or low response to training		
Diet History		
Food frequency questionnaire	X	X
24-hour diet recall	X	X
Gut Microbiota		
Diversity	X	X
Short chain fatty acid	X	X
Body Composition		
Weight	X	X

Body mass index	X	X
Waist circumference	X	X
Body fat percentage	X	X
Blood chemistry		
Total Cholesterol	X	X
HDL	X	X
LDL	X	X
Triglycerides	X	X
Glucose	X	X
DNA	X	
Family and Personal Medical History		
Family History of Cardiovascular Disease	X	
History of Illness or Injury	X	
Smoking status	X	
Medications	X	
Exercise habits	X	
CESD-R score	X	X

Statistical Analysis

Determining the association between the gene predictor score and the gut microbiome

Following on from the GWAS, a genetic predisposition score for each participant will be calculated to test for the cumulative effect of multiple alleles on $\dot{V}O_{2peak}$ training response and cardiovascular disease risk factors. Using the genetic variants identified from our PREDICT HIIT study (results yet to be published) and taking the approach used in Thomaes et al. (2011), '0' will be given for a homozygote for alleles associated with a low response to training, '1' for heterozygote for an allele associated with high response, and '2' for homozygotes of an allele associated with high response to training. The $\dot{V}O_{2max}$ scores and other covariates will be collated for each participant. Microba will provide gut bioinformatics for each participant (pre and post intervention). The butyrate production per participant will also be calculated as described above (pre and post intervention). This information (including average fibre intake per participant) will be analysed using SPSS statistical software (IBM SPSS Statistics).

Data will be tested for normality using a Shapiro-Wilk test. Where normality is not found, the Kruskal-Wallis test will be used for comparing between data sets.

To compare the mean OTUs (and other bioinformatics provided by 'Microba'), fibre intake and butyrate production for predicted low and high responders (e.g. gene predictor score), a one-way analysis of co-variance (ANCOVA) will be calculated (with age and sex as covariates).

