Investigating whether altering the gut microbiome via diet and training influences the $\dot{V}O_{2max}$ training response to HIIT

The change in $\dot{V}O_{2max}$ of each participant will be calculated. Low responders will be classified by a $\dot{V}O_{2peak}$ change of <100ml of O_2 /min, and high responders by a $\dot{V}O_{2peak}$ change of > 700ml in O_2 /min (following the intervention period).

To compare the mean change in OTUs, alpha diversity, fibre intake and butyrate production to $\dot{V}O_{2max}$ training response, a one-way analysis of co-variance (ANCOVA) will be calculated (with age, sex, baseline $\dot{V}O_{2max}$ as covariates).

A multiple regression analysis will be used to evaluate the role of possible predictors for change in $\dot{V}O_{2max}$. Predictors will be screened using a Spearman correlation matrix to find the top four significant variables to include in the multiple regression analysis (e.g. gene predictor score, sex, age, gender, BMI, fibre intake, OTUs, butyrate production, alpha diversity).

The above approach will also be used to compare changes in other biomarkers (e.g. blood tests, body fat percentage etc).

All statistical tests will be performed at a 5% significance level.

1. Montero, D. and C. Lundby, *Refuting the myth of non-response to exercise training: 'non-responders' do respond to higher dose of training*. JAP, 2017.
2. Mann, T., R. Lamberts, and M. Lambert, *High responders and low responders: factors associated with individual variation in response to standardized training*. Sports Med, 2014. **44**(8): p. 1113-1124.
3. Bouchard, C., et al., *Personalized preventive medicine: genetics and the response to regular exercise in preventive interventions*. Prog Cardiovasc Dis, 2015. **57**(4): p. 337-46.
4. Rankinen, T. and C. Bouchard, *Genetic predictors of exercise training response*. Current Cardiovascular Risk Reports, 2011. **5**(4): p. 368-372.
6. Williams, C., et al., *Genes to predict VO2max trainability: a systematic review*. BMC Genomics, 2017. **18**(Suppl 8:831).
7. Astorino, T. and M. Schubert, *Individual responses to completion of short-term and chronic interval training: a retrospective study*. PLoS One, 2014. **9**(5): p. e97638.

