APPENDIX

1. Adult Pre-Exercise Screening Tool

<https://www.essa.org.au/wp-content/uploads/2011/09/Screen-tool-version-v1.1.pdf>

2. *Microba* online questionnaires (already approved through their ethics committee)

a) Sample food frequency questionnaire

https://www.cancervic.org.au/downloads/cec/FFQs/DQES_v2_Sample-Questionnaire.pdf

b) Medical history

General

What is your date of birth?	Month	Number
What is your date of birth?	Day	Number
What is your date of birth?	Year	Number
What is your biological sex?	choice	Male
What is your biological sex?	choice	Female
What is your biological sex?	choice	Intersex
How would you describe your ethnicity?	choice	Aboriginal
How would you describe your ethnicity?	choice	African
How would you describe your ethnicity?	choice	East Asian
How would you describe your ethnicity?	choice	South Asian
How would you describe your ethnicity?	choice	European
How would you describe your ethnicity?	choice	Mixed North American
How would you describe your ethnicity?	choice	Latino
How would you describe your ethnicity?	choice	Middle Eastern
How would you describe your ethnicity?	choice	Polynesian
How would you describe your ethnicity?	choice	Mixed
How would you describe your ethnicity?	choice	Other (please specify)
Please specify Other ethnicity		NULL
What is your height (in cm)?	number	NULL
What is your weight (in kg)?	number	NULL
Are you now married, living with a partner in a marriage-like relationship, widowed, divorced, separated, or never married?	choice	Married
Are you now married, living with a partner in a marriage-like relationship, widowed, divorced, separated, or never married?	choice	Living with partner
Are you now married, living with a partner in a marriage-like relationship, widowed, divorced, separated, or never married?	choice	Widowed

Are you now married, living with a partner in a marriage-like relationship, widowed, divorced, separated, or never married?	choice	Divorced
Are you now married, living with a partner in a marriage-like relationship, widowed, divorced, separated, or never married?	choice	Separated
Are you now married, living with a partner in a marriage-like relationship, widowed, divorced, separated, or never married?	choice	Never married
What is the highest level of education you completed?	choice	Less than high school
What is the highest level of education you completed?	choice	High school
What is the highest level of education you completed?	choice	Professional certification

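### The comparison of gut measures between predicted low and high responders fixes age and sex as covariates and omits ancestry, so in a mixed sample an ancestry difference can appear as a gene-gut link

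*Protocol*

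**What the plan says.** - **The test.** Protocol, Statistical Analysis, first subsection (gene predictor score and gut microbiome): mean OTUs, fibre intake and "butyrate production for predicted low and high responders (e.g. gene predictor score") are compared, and "a one-way analysis of co-variance (ANCOVA) will be calculated (with age and sex as covariates"). A score is to be calculated for every participant, following on from the GWAS.
- **The fallback.** Same subsection: "Where normality is not found, the Kruskal-Wallis test will be used for comparing between data sets". That test takes no covariates.
- **The grouping.** Background, section on predictor genes, gives an example cut: "Individuals with a low score (e.g. <9 high response alleles) may be a lower responder to training".
- **Ancestry in the genome scan.** Data Collection, GWAS analysis, step c: ancestry is one of the sample-level filters, with no threshold or reference group stated. The step also creates "principal components for capturing population-substructure", and these enter the scan's logistic regression. No other analysis is said to use them.
- **The sample.** Recruitment is to "continue until 40 people have been recruited". The inclusion and exclusion criteria do not mention ancestry. The online medical-history form (Appendix, item 2b) asks "How would you describe your ethnicity".
- **The regression for VO2max change.** Statistical Analysis, second subsection: the example candidate predictors are "gene predictor score, sex, age, gender, BMI, fibre intake, OTUs, butyrate production, alpha diversity". Ancestry is not among them.

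**The concern.** The groups in this ANCOVA are defined by genotype, so randomisation does not balance them. Allele frequencies can differ between ancestry groups, and a score that counts alleles can differ with them. Habitual diet and gut composition can differ too. The protocol itself says that diet shapes the microbiome, and fibre intake is one of the outcomes compared. Ancestry is therefore a possible common cause of group membership and outcome. Age and sex do not cause an autosomal genotype, so adjusting for them does not close this path.

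The protocol recognises the problem for the genome scan, yet tests a score built from the same genotypes without the same protection. The protocol itself states the covariate list, so this is more than a detail left to a later analysis plan.

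At stake is the first secondary hypothesis, that the gene score correlates with gut taxa. In a mixed sample, a positive result could not be told apart from population structure.

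**Working it through.** **1. The protocol's own figure.** The Power Calculation section gives f² = 0.22, alpha 0.05, numerator df 1, 6 predictors and N = 39. Then λ = 0.22 × 39 = 8.58 and denominator df = 39 − 6 − 1 = 32. The critical F is 4.149 and power is 0.8106, as stated. N = 38 gives 0.7998, so 39 is the smallest adequate N. This calculation is for the VO2max regression; it is used here only to price extra covariates.

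**2. Size of the spurious association.** The documents give no ancestry share and no shift, so these are assumptions. Let a share q belong to a second ancestry group in which score and gut measure are both shifted by d SD, with no link within either group. The induced correlation is d²q(1−q) / [1 + d²q(1−q)]:
- q = 0.30, d = 0.5: 0.0525/1.0525 = 0.05
- q = 0.20, d = 1.0: 0.16/1.16 = 0.14
- q = 0.30, d = 1.0: 0.21/1.21 = 0.17
- q = 0.30, d = 1.5: 0.4725/1.4725 = 0.32

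**3. False-positive rate of the planned test.** Simulation with N = 40: score = N(0,1) + d × ancestry, gut = N(0,1) + d × ancestry, and gut regressed on score, age and sex, at least 3,000 repetitions per setting in the main runs. The split at the median stands for the grouped comparison that the protocol plans.

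| Minority share | Shift (score, gut) | Split score, age and sex |
|---|---|---|
| 10% | 1.0, 1.0 SD | 6% |
| 20-30% | 0.5, 0.5 SD | 5-6% |
| 30% | 1.0, 0.5 SD | about 7.5% |
| 20% | 1.0, 1.0 SD | 9-10% |
| 40% | 0.8, 0.8 SD | 10-11% |
| 30% | 1.0, 1.0 SD | 13-14% |
| 30% | 1.5, 1.5 SD | about 38% |

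With an ancestry indicator added, every setting returns to about 5%. Two further corners, run with 10,000 repetitions, gave 7% (20%, 0.8 SD) and 17% (40%, 1.0 SD). Entering the score as a number raises the rates, for example to 19% at 30% with 1.0 SD and 53% at 30% with 1.5 SD, but that is not the comparison stated.

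**4. A second model.** The score is a sum of 18 alleles split at 9. The high-response allele frequency is 0.5 in the majority and 0.4 or 0.3 in the minority, and the gut shift is 0.5 or 1.0 SD (4,000 repetitions). The error with age and sex is 4.7% with no mix, 5.6-9.0% at a 10% minority, 5.9-16.2% at 20%, 7.2-24.9% at 30% and 7.8-30.0% at 40%. With ancestry added it is 4.4-5.8%. The upper ends are demanding. The score SD is √(18 × 0.5 × 0.5) = 2.12, so a frequency gap of 0.2 at all loci, in the same direction, shifts the score by 3.6 alleles, or 3.6/2.12 = 1.7 SD.

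**5. What age and sex do.** In the second model at a 20% minority, gap 0.2 and 1.0 SD, the error is 17.3% with no covariates, 16.2% with age and sex, and 5.4% with ancestry added.

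**6. Price of the correction.** With 8 predictors instead of 6 at unchanged f², power goes from 0.811 to 0.809. If 0.22 is the effect before adjustment and ancestry explains a share R² of the score, f² becomes 0.22 × (1 − R²). With the values of step 2, which equal R² under this model, 0.22 × 0.86 = 0.19 gives power of about 0.75, 0.22 × 0.83 = 0.18 gives 0.73, and 0.22 × 0.68 = 0.15 gives 0.65.

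**The case against.** **The questionnaire.** A reader might infer from the ethnicity options that a mixed sample is expected. The documents do not support that. It is the vendor's generic form, and it also lists pregnancy, diabetes and Crohn's disease, all of which exclude a participant here. It shows that ethnicity is recorded, not what the mix will be.

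**The filter.** Because the score follows on from the GWAS, samples that fail the ancestry filter may never be scored. A strict filter carried through would remove much of the mix, at the price of fewer than 40 people. This reading is open. The text neither confirms it nor gives a threshold, so clarification is part of the remedy.

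**The size.** All rates rest on assumed shares and shifts, mostly equal for score and gut. With a small minority or modest shifts the inflation is negligible. A reader might take away that half of such tests would be false positives, but that needs a numeric score, a 30% minority and 1.5 SD on both variables. Nothing in the documents supports shifts of that size for a score whose variants are still unpublished.

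**Age and sex.** A reader might infer that they are wrong covariates. They are not: they are ordinary precision covariates for a gut outcome and should stay.

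**The VO2max regression.** A reader might extend the bias to it. The predictor list there is only an example, the score enters only if it survives the screen to four variables, and bias would also need ancestry to affect VO2max change, which has not been shown.

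**Importance.** This is a secondary aim of a pilot study. With many gut measures each tested at 5%, false claims remain possible after this correction.

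What stands is that the covariate list is fixed, it omits the one confounder that the protocol handles elsewhere, and nothing carries that handling across.

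**Conclusion.** The point holds in a conditional form. As written, the ANCOVA between genotype-defined groups has no protection against ancestry confounding unless the scan's filter is strict and also defines the scored set. If the sample is mixed, the error for the planned grouped comparison lies between barely above nominal and about 9-14% in the moderate settings listed; about 38% needs a 30% minority with 1.5 SD shifts. An ancestry term brings it back to about 5% in every setting tried. These figures rest on two ancestry groups, no link within either, N = 40 and assumed shifts. The real mix and shifts are unknown, so the actual bias could be nil.

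The randomised prebiotic-placebo comparison is not affected, and nothing here bears on the primary aim. The change is worth making because it is cheap and decides whether a positive gene-gut finding can be interpreted.

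**What to change.** In the first subsection of Statistical Analysis:

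- Keep age and sex, and add the first two principal components already planned in the GWAS step. Alternatively, use self-reported ethnicity collapsed to a few groups; the form has 11 categories, which would use up to 10 degrees of freedom uncollapsed.
- State whether the GWAS ancestry filter defines the participants who are scored and analysed, and on what threshold.
- Add one sensitivity analysis in the largest ancestry group.
- Since Kruskal-Wallis cannot carry covariates, say how a non-normal gut measure will be adjusted, for example by ANCOVA on a transformed or ranked outcome.
- If the gene score enters the VO2max-change regression, include the same ancestry terms there.

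Cost: no new data. Two components use two degrees of freedom (power 0.811 to 0.809 on the protocol's formula at unchanged f²). Where ancestry explains part of the score, power falls further, to about 0.75, 0.73 or 0.65 in the settings of step 6. Components from only 40 people are unstable; projecting them on a reference panel would help but is an extra step that the protocol does not plan.

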Our gut microbiome is predetermined by host genetics that can be manipulated through numerous external factors, such as exercise and diet. Whilst host genetics and associated gut taxa increases susceptibility to various chronic diseases and overall fitness levels, the relationship between the gut microbiome and $\dot{V}O_{2max}$ trainability is unknown.

In addition to examining the gene predictor score for $\dot{V}O_{2max}$ trainability, our study will also investigate microbiota-related genes, host genes related to gut microbiome composition, and the genes involved with the gut-microbiota cross-talk. In conclusion, we hope to collect data to help understand if manipulation of the gut microbiome can improve the training response of individuals with a low gene predictor score for $\dot{V}O_{2max}$ trainability.

RESEARCH PLAN

Improving High Intensity Interval Training Response (IMPROVE-HIIT)

Overview

Improve HIIT will examine the association between the gene predictor score for $\dot{V}O_{2max}$ trainability the gut microbiome; and to investigate whether altering the gut microbiome via diet and training influences the $\dot{V}O_{2max}$ training response to HIIT.

Design

Improve HIIT is an 8-week randomised trial with two groups allocated to either: (1) HIIT plus placebo; or (2) HIIT plus prebiotic

Study Population

Consenting adults aged over 18 years.

Power Calculation (sample size justification)

The proposed project will be a pilot study. Considering financial resources, a sample size of 40 is possible. When using G*Power (download.cnet.com) ([52]), a sample size of 39 will achieve a medium effect size of 0.22 (using 6 predictors). This participant number is similar to a previous study examining if gut taxa is related to $\dot{V}O_{2max}$ levels [12]. A linear multiple regression model was used to include covariates that may contribute to the overall outcome (e.g. 6 predictors may include BMI, age, gender, initial $\dot{V}O_{2max}$, initial gut microbiome and cholesterol levels). Below are results of the power calculation:

F tests - Multiple Regression: Special (R^2 increase)

Analysis: A priori: Compute required sample size

Input:	Effect size f^2	= 0.22
	α err prob	= 0.05
	Power (1- β err prob)	= 0.8
	Numerator df	= 1
	Number of predictors	= 6
Output:	Noncentrality parameter λ	= 8.58
	Critical F	= 4.149097
	Denominator df	= 32
	Total sample size	= 39
	Actual power	= 0.8106

Recruitment

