Change in cardiorespiratory fitness

An incremental treadmill test to exhaustion on a treadmill will be completed at baseline and 6 weeks to ascertain $\dot{V}O_{2peak}$. This test involves the participant wearing a head and mouthpiece, nose tape and nose clip. The participant walking on a treadmill at 0% gradient and 1.6km/hour (Bruce Ramp). This initial stage is used as the warm up period. During the test, speed and gradient is monitored. Heart rate and rating of perceived exhaustion is measured at the end of every minute. The speed and or gradient of the treadmill is increased every one-minute. Expired air is collected via a metabolic cart every 30 seconds during the test. Heart rate is measured via a Polar heart rate monitor and blood pressure is taken using a sphygmomanometer. The participant is encouraged to exercise until exhaustion. At exhaustion, the grade, speed and heart rate are recorded. The workload is decreased to 3km/hour with no incline to allow the participant to cool down. Following the cool down, the test is ended, and all devices are removed from the participant. $\dot{V}O_{2peak}$ is measured as the average of the two highest volumes of oxygen consumed (reported as volume per minute relative to body weight; mL/kg/min).

STAGE	TIME (min)	GRADE (%)	SPEED (km/hr)
1	1	0	1.6
2	1	5	2.1
3	1	10	2.7
4	1	10	3.4
5	1	11	3.7
6	1	12	4.0
7	1	12	4.2
8	1	13	5.0
9	1	14	5.4
10	1	14	6.1
11	1	15	6.6
12	1	16	6.7
13	1	16	7.2
14	1	17	7.7
15	1	18	8.0
16	1	18	8.5

Figure 2. VO_{2peak} test stages

Gut microbiota

Gut diversity/bioinformatics and short-chain fatty acid (SCFA) analysis will be performed on faecal samples collected at baseline and 6 weeks. Participants will be provided with a home stool collection kit with instructions. They will be asked to keep stool sample frozen until their next testing visit. After this time, the stool samples will be kept at -80 degrees Celsius until analysis. One stool sample will be kept for short chain fatty acid analysis, and two other stool samples will be sent to *Microba* for testing.

a) Short chain fatty acid analysis

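### The responder cut-offs (<100 and >700 mL O2/min) leave 100-700 mL/min without a class and are on a different scale from the mL/kg/min outcome; response should be analysed as a continuous change

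*Protocol*

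**What the plan says.** The second part of the protocol's Statistical Analysis section deals with the training response. It first calculates each participant's change in VO2max. It then defines two classes only. For the low class the wording is "change of <100ml of O_2 /min, and high responders by a"; the sentence at that point turns to the high class, and the limit it sets there is a "change of > 700ml in O_2 /min (following the intervention period"). No class is named for a change between the two limits, and nothing says whether those participants are dropped, pooled or treated as a third group.

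The next paragraph plans a one-way ANCOVA relating changes in OTUs, alpha diversity, fibre intake and butyrate production to the training response, with age, sex and baseline VO2max as covariates. A multiple regression for change in VO2max follows. The same approach is then extended to other biomarkers.

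Under Change in cardiorespiratory fitness, VO2peak is defined on another scale: "reported as volume per minute relative to body weight; mL/kg/min".

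Three other places bear on the point:
- The Secondary Hypotheses include one that the gene predictor score will separate lower from higher responders.
- The GWAS paragraph says "Logistic regression will be performed with 'N' PCA components (N is unknown until we do the experiments") and names no outcome for that model.
- The Power Calculation states that "Considering financial resources, a sample size of 40 is possible" and that "a sample size of 39 will achieve a medium effect size of 0.22 (using 6 predictors").

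**The concern.** A one-way ANCOVA needs a grouping factor. The only groups that the protocol builds from the measured response are these two extremes, 600 mL/min apart. If they are the factor, the handling of everyone in between decides how many of the 40 participants contribute, and the protocol is silent on it. With a very small or empty high group, the contrast would have little power or could not be estimated.

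The scale is a separate problem. A fixed number of mL/min is a larger relative gain in a light person than in a heavy one, and the two scales can disagree within one person when weight changes during the study. Responder status would then carry information on body mass into its association with genes and microbiome. The ANCOVA adjusts for sex and baseline VO2max, but not for weight.

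**Working it through.** **1. The plan's own figure.** The sample size uses "F tests - Multiple Regression: Special (R^2 increase") with f² = 0.22, 6 predictors, numerator df 1 and α = 0.05. For N = 39:
- denominator df = 39 − 6 − 1 = 32
- λ = 39 × 0.22 = 8.58
- critical F = 4.149
- power = 0.8106

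All of these match the protocol. With all 40 participants, λ = 8.80 and power = 0.821. The cut-offs do not enter this calculation.

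**2. Expected class sizes.** The protocol gives no mean or SD for the change in absolute VO2peak, so both are assumed here: mean m of 200-500 mL/min, SD s of 150-250 mL/min, normal distribution. Then
- P(low) = Φ((100 − m)/s)
- P(high) = 1 − Φ((700 − m)/s)
- P(unassigned) = 1 − P(low) − P(high)
- P(no high responder among 40) = (1 − P(high))^40

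| Mean / SD (mL/min) | Low of 40 | Unassigned of 40 | High of 40 | Unassigned share | P(no high) |
|---|---|---|---|---|---|
| 200 / 150 | 10.1 | 29.9 | 0.0 | 75% | 0.98 |
| 200 / 250 | 13.8 | 25.3 | 0.9 | 63% | 0.40 |
| 300 / 200 | 6.3 | 32.7 | 0.9 | 82% | 0.40 |
| 400 / 150 | 0.9 | 38.2 | 0.9 | 95% | 0.40 |
| 400 / 200 | 2.7 | 34.7 | 2.7 | 87% | 0.06 |
| 500 / 150 | 0.2 | 36.2 | 3.6 | 90% | 0.02 |
| 500 / 250 | 2.2 | 29.3 | 8.5 | 73% | <0.001 |

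The unassigned share runs from 63% to 95%. Widening the SD to 100-300 gives 58% to 99.7%, or about 23 to 40 of 40.

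**3. Where this stops holding.** At a mean of 100 mL/min, half of the participants are already low responders, so the unassigned share is 50% or less. At higher means, it falls below half only once the SD reaches about 350 (mean 150), 400 (mean 200), 440 (mean 300) or 450 (mean 400).

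**4. Scale.** Dividing the cut-offs by body weight (illustrative weights):
- 700/65 = 10.8 and 700/85 = 8.2 mL/kg/min
- 100/65 = 1.5 and 100/85 = 1.2 mL/kg/min

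Within one person: going from 2,400 to 2,490 mL/min while weight falls from 80 to 78 kg is +90 mL/min, a low response. On the reported scale it is 2,490/78 − 2,400/80 = 31.92 − 30.00 = +1.92 mL/kg/min. That exceeds the low cut-off at 80 kg, 100/80 = 1.25 mL/kg/min.

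**5. What a contrast of the extremes could detect.** For two equal groups, the protocol's f² = 0.22 corresponds to a standardised difference d = 2√0.22 ≈ 0.94. With three covariates, df = n_low + n_high − 5 and noncentrality = d × √(n_low × n_high/(n_low + n_high)). Two-sided power at 5% for assumed group sizes is:
- 10 v 2: 0.18
- 12 v 3: 0.26
- all 40 split 20 v 20: 0.82

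**The case against.** The strongest reply is that much of the plan does not use these cut-offs. The multiple regression already takes change in VO2max as it stands. The ANCOVA in the first part of the Statistical Analysis groups people by gene score. The sample size rests on a regression test. The trial is a self-described pilot, and its primary aim concerns the prebiotic. All of this stands, and it limits the reach of the point.

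It can also be said that the text never names the two classes as the ANCOVA factor and never says the middle band is excluded. A three-level factor would keep everyone and would fit the wording. That too is right. A reader might infer that most participants will be discarded and that the response analyses rest on a handful of people, but the protocol does not establish either. Exclusion is an inference, and the class sizes need an assumed mean and SD. Within the assumptions above, the low group can reach about 14 and the high group about 8 or 9.

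A reader might also infer that the logistic GWAS depends on these classes. The GWAS paragraph names no outcome, and the gene score is built from variants found in a separate study, so this is not supported either.

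On scale, sex and baseline VO2max are already covariates, which deals with part of the sex difference. Weight is measured before and after, so absolute values can be recovered. Neither removes the dependence on body mass or on weight change.

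What remains is fixed by the protocol itself: two limits, an unnamed band between them, and a scale that differs from that of the outcome.

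**Conclusion.** The point holds in a limited form. Two parts need no assumption: changes of 100-700 mL/min have no class, and the classes are in mL/min while the outcome is in mL/kg/min. That these classes are the factor in the training-response ANCOVA, and the groups meant in the responder hypothesis, is likely because no other outcome-based groups are defined, but it is not stated.

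The size is conditional. With a mean gain of 200-500 mL/min and an SD of 150-250, about 63-95% of 40 participants would probably be unassigned. At a mean of 300 and an SD of 200, that is about 6 low, 33 unassigned and 1 high, with a 40% chance of no high responder. A mean of about 100 or less, or an SD of about 350-450 or more, would overturn the statement that most are unassigned. The consequence is a weak or unworkable low-versus-high comparison. The trial as a whole is not underpowered because of it.

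**What to change.** In the training-response part of the Statistical Analysis and in the test of the gene-score hypothesis, replace the low/high factor with change in VO2peak as a continuous variable, in mL/kg/min as defined under Change in cardiorespiratory fitness. Include all participants with data and keep baseline VO2peak as a covariate. Suggested text:

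*Training response is the change in VO2peak (mL/kg/min), analysed as a continuous variable with adjustment for baseline VO2peak, age and sex. Low, middle and high response classes, defined on one stated scale and covering all values, are reported as counts only.*

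The GWAS paragraph should name its outcome. If that outcome is meant to be the training response, use linear regression on the continuous change in place of logistic regression.

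The cost is small but is more than a change to one sentence. The hypothesis on lower and higher responders must be reworded as an association between the gene score and the continuous response, and the responder labels become descriptive. No measurement, visit or participant is added, and the sample-size calculation stays as it is.
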